### **Chest X-Ray (CXR)**

A CXR (posterior-anterior and lateral views) is required:

- For all subjects at Screening to rule out the presence of TB or other clinically relevant findings. The CXR will not be required if the subject had a previous normal CXR (posterior-anterior and lateral views) within 90 days of Screening, provided all source documentation is available at the site as outlined below and provided nothing has changed in the subject's medical history to warrant a repeat test.

- Annually for subjects with newly identified TB risk factors as determined by the TB risk assessment form ([Appendix I](#)) or for subjects living in areas endemic for TB or for subjects with newly positive PPD and/or QuantiFERON-TB Gold test.

Due to a state of emergency or pandemic situation like COVID-19, subject visits may be conducted via phone or video conference. In these situations, if a visit requires completion of a CXR, the CXR will be performed at the next earliest feasible visit, unless the Investigator has determined, based on clinical judgement, that a CXR is required to ensure that it is safe to continue study drug administration. In this case, CXR should be performed as soon as restrictions allow at the study site or local hospital/facility.

Subjects can have a repeat CXR at any time during the study as warranted, based on the opinion of the Investigator.

A radiologist or pulmonologist must perform an assessment of the CXR. The Principal Investigator will indicate the clinical significance of any findings and will sign and date the report. In the assessment of the CXR, the Principal Investigator or his/her delegate must indicate the presence or absence of (1) calcified granulomas, (2) pleural scarring/thickening, and (3) signs of active TB. If the CXR demonstrates changes suggestive of previous TB (e.g., calcified nodule, fibrotic scar, apical or basilar pleural thickening) or other findings that are clinically significant, the Principal Investigator should contact the AbbVie Therapeutic Area Medical Director before enrolling the subject.

### **12-Lead ECG**

For all subjects, a resting 12-lead ECG will be performed at Screening and every 48 weeks thereafter, as specified in [Appendix D](#) and [Appendix F](#). A qualified physician will interpret the clinical significance of any abnormal finding, sign, and date each ECG. ECG with QT interval corrected for heart rate using Fridericia's correction formula (QTcF) should be reported (or calculated) and documented in the source documents and later transcribed on to the appropriate eCRF if QTcF prolongation is observed. A valid QTcF cannot be calculated in subjects who have a pacemaker or supraventricular or

ventricular conduction abnormalities. In case of QTcF prolongation, the baseline QTcF will need to be entered into the appropriate eCRF for comparison as well. In addition, any clinically significant findings will be documented in the source documents and later transcribed on to the appropriate eCRF. Each signed original ECG will be monitored by the responsible site monitor and kept with subject's source documents onsite.

For subjects with a normal ECG taken within 90 days of Screening, a repeat ECG at Screening will not be required, provided source documentation is available and provided nothing has changed in the subject's medical history to warrant a repeat test. If there are other findings that are clinically significant, the Investigator must contact the AbbVie Therapeutic Area Medical Director before enrolling the subject.

Subjects can have a repeat ECG at any time during the study as warranted, based on the opinion of the Investigator.

Due to a state of emergency or pandemic situation like COVID-19, subject visits may be conducted via phone or video conference. In these situations, if a visit requires completion of an ECG, the ECG will be performed at the next earliest feasible visit, unless the Investigator has determined, based on clinical judgement, that an ECG is required to ensure that it is safe to continue study drug administration. In this case, the ECG should be performed as soon as restrictions allow at the study site or local hospital/facility.

### **X-Rays of Hands and Feet**

Detailed instructions for performing and transmitting the study related x-rays of hands and feet are provided in a separate Imaging Acquisition Guideline (IAG)/Site Operational Manual.

#### *Handling of X-Rays of Hands and Feet at Screening*

Screening x-rays of bilateral hands (posterior-anterior view) and bilateral feet (anteroposterior view) must be performed within the 35-day screening period.

Once a subject has been deemed eligible to participate and has had screening x-rays performed, the x-rays will be sent to the central imaging laboratory designated by the Sponsor. Digitalized images may be acceptable, provided that they meet the specifications outlined in the IAG/Site Operations Manual. X-rays not meeting the quality requirements must be repeated within the 35-day screening window. Subjects can receive the first dose of study drug if the x-rays have been determined to be of sufficient quality by the central imaging laboratory.

Screening x-rays of hands and feet will serve as baseline x-rays for scoring purposes.

Joint x-rays will be sent to the central imaging vendor designated by the Sponsor. The x-rays will only be assessed by the imaging vendor for erosions and joint space narrowing, and will not be assessed for any other clinically significant findings that may impact a subject's health.

#### *Handling of X-Rays of Hands and Feet after Baseline*

Handling of x-rays of hands and feet after baseline in Period 1 is illustrated in [Figure 3](#).

All subjects (regardless of response) will receive Week 24 x-rays ([Figure 3](#), box A) and Week 48 x-rays ([Figure 3](#), box B).

If a subject prematurely discontinues from the study (withdrawal of informed consent), depending on the time of discontinuation, new x-rays might be needed.

- Subjects who prematurely discontinue before Week 12 will not get x-rays ([Figure 3](#), box C)
- Subjects who prematurely discontinue from Week 12 to before Week 24 ( $\geq$  Week 12 and  $<$  Week 24), will have new x-rays performed ([Figure 3](#), box D).
- Subjects who prematurely discontinue after Week 24 to before Week 36 ( $>$  Week 24 and  $<$  Week 36), will not have x-rays performed ([Figure 3](#), box E).

- Subjects who prematurely discontinue from Week 36 to before Week 48 ( $\geq$  Week 36 and  $<$  Week 48), will have new x-rays performed (Figure 3, box F).

If a subject prematurely discontinues from study drug but continues to participate in the study, subject should follow the regular visit schedule as outlined in Appendix D and Appendix F, including performance of scheduled x-rays of hands and feet. However, depending on the time of study drug discontinuation in Period 1, new x-rays might be needed.

- Subjects who prematurely discontinue from study drug before Week 12 will not get new x-rays.
- Subjects who prematurely discontinue from study drug from Week 12 to Week 16 ( $\geq$  Week 12 and  $\leq$  Week 16), will have new x-rays performed.
- Subjects who prematurely discontinue from study drug after Week 16 to Week 24 ( $>$  Week 16 and  $\leq$  Week 24), will have x-rays performed at Week 24 (standard).
- Subjects who prematurely discontinue from study drug after Week 24 to Week 36 ( $>$  Week 24 and  $<$  Week 36), will not have new x-rays performed.
- Subjects who prematurely discontinue from study drug from Week 36 to Week 40 ( $\geq$  Week 36 and  $\leq$  Week 40), will have new x-rays performed.
- Subjects who prematurely discontinue from study drug after Week 40 to Week 48 ( $>$  Week 40 and  $\leq$  Week 48), will have x-rays performed at Week 48 (standard).

X-rays will be sent to the central imaging laboratory designated by the Sponsor.

Digitalized images may be acceptable, provided that they meet the specifications outlined in the IAG/Site Operations Manual. X-rays not meeting the quality requirements must be repeated.

[figure not shown]
Overall in Period 1, each subject will undergo a maximum of 3 scheduled visits for x-ray examination of bilateral hands and feet (unless unscheduled repeat imaging is needed due

to failure to meet the quality requirements) at Screening, Week 24, and Week 48/PD. One additional x-ray examination of bilateral hands and feet may be needed depending on the time of premature study drug discontinuation for those subjects that continue the study.

In Period 2, a follow-up x-ray of hands and feet is planned at Week 96, Week 192, and Week 260. Subjects who prematurely discontinue from Period 2 will undergo an x-ray of hands and feet unless the previous x-ray was performed within the previous 24 weeks. Images will be sent to the central imaging laboratory designated by the Sponsor.

Due to a state of emergency or pandemic situation like COVID-19, subject visits may be conducted via phone or video conference. In these situations, if a visit by phone or video conference occurs at one of the designated study visits specified to complete x-rays of hands and feet, it will be performed at the next earliest feasible visit.

**Figure 3. Handling of X-Rays of Hands and Feet after Baseline (Period 1)**

MTX = methotrexate; n = number; PD = premature discontinuation; QD = once daily; SJC = swollen joint count; TJC = tender joint count; W = week

\* Subjects who prematurely discontinue from the study drug from Week 12 to Week 16 ( $\geq$  Week 12 and  $\leq$  Week 16) or from Week 36 to Week 40 ( $\geq$  Week 36 and  $\leq$  Week 40), but continue to participate in the study will have new x-rays performed.

### Height and Weight

Height will be measured at the Screening Visit only (with shoes off). Body weight will be measured at all scheduled visits as specified in [Appendix D](#) and [Appendix F](#). All measurements will be recorded in metric units where applicable.

### **Vital Signs**

Vital sign determinations of systolic and diastolic blood pressure in sitting position, pulse rate, respiratory rate, and body temperature will be obtained at visits specified in [Appendix D](#) and [Appendix F](#). Blood pressure, pulse rate, body temperature, and respiratory rate should be performed before blood draws are performed.

### **Physical Examination**

A complete physical examination will be performed at the designated study visits as specified in [Appendix D](#) and [Appendix F](#). The physical examination at the Baseline Visit will serve as the baseline physical examination for the entire study. Physical examination abnormalities noted by the Investigator at Baseline prior to the first dose of study drug will be recorded in the subject's medical history; abnormalities noted after the first dose of study drug will be evaluated and documented by the Investigator as to whether or not the abnormality is an AE (see Section 6.1.1.1 for AE definition). All findings whether related to an AE or part of each subject's medical history will be captured on the appropriate eCRF page.

Due to a state of emergency or pandemic situation like COVID-19, subject visits may be conducted via phone or video conference. In these situations, if a visit by phone or video conference occurs at one of the designated study visits specified to complete physical examination, the complete physical examination will be performed at the next feasible visit.

At any time, a symptom-directed physical examination can be performed as deemed necessary by the Investigator.

### **Physician Global Assessment of Disease Activity VAS**

At visits specified in [Appendix D](#) and [Appendix F](#), the Physician will rate global assessment of subject's current disease activity ranging from 0 to 100 independent of the subject's self-assessment using the VAS, which consists of a horizontal 100 mm line

anchored at either end by opposite adjectives reflecting the spectrum/severity of the parameters assessed ([Appendix G](#)).

Due to a state of emergency or pandemic situation like COVID-19, subject visits may be conducted via phone or video conference. In these situations, the Physician Global Assessment of Disease Activity will be completed by the physician at the next feasible visit.

### **TJC and SJC Assessment**

#### *TJC Assessment*

An assessment of 68 joints ([Appendix H](#)) will be done for tenderness by pressure manipulation on physical examination at visits specified in [Appendix D](#) and [Appendix F](#). Joint pain/tenderness will be classified as: present ("1"), absent ("0"), replaced ("9") or no assessment ("NA").

#### *SJC Assessment*

An assessment of 66 joints ([Appendix H](#)) will be done by directed physical examination at visits specified in [Appendix D](#) and [Appendix F](#). The joints to be examined for swelling are the same as those examined for tenderness, except the hip joints are excluded. Joint swelling will be classified as present ("1"), absent ("0"), replaced ("9") or no assessment ("NA").

Any injected joints will be considered as "not assessed" ("NA") for 3 months from the time of the intra-articular injection.

If possible, the TJC and SJC should be performed by an independent and blinded joint assessor who should not perform any other study related procedures.

In order to minimize variability, the same independent joint assessor should evaluate the subject at each visit for the duration of the trial as much as possible. A back-up independent joint assessor should be identified. The independent joint assessors should

be a qualified medical professional (e.g., nurse, physician's assistant, physician). Any other joint assessor must be trained and competent in performing such assessments. It is the responsibility of the Investigator to ensure that all assessors are qualified and trained to perform joint assessments. If the independent assessor is not available, the pre-identified back-up assessor should perform such assessments.

Due to a state of emergency or pandemic situation like COVID-19, subject visits may be conducted via phone or video conference. In these situations, the TJC and SJC will be performed at the next feasible visit by the independent joint assessor, if possible.

### **CDAI**

The CDAI calculation is required to determine if a subject fails to achieve Clinical Remission at the Week 26 visit. An Interactive Response Technology (IRT) will calculate CDAI with input from site personnel on joint counts and the subject's and physician's Global Assessment of RA Disease Activity score. A worksheet will be provided to capture the components required for IRT entry to obtain the CDAI calculation.

The calculation used to determine CDAI score at Week 26 is as follows:

$$\text{CDAI} = \text{TJC28} + \text{SJC28} + \text{PtGA} + \text{PhGA}$$

NOTE: As described in the section pertaining to Rescue Therapy, the Investigator should optimize background RA therapies in subjects who fail to achieve a  $\text{CDAI} \leq 2.8$  at Week 26, but achieve at least 20% improvement in both TJC and SJC.

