### **5.3.3 Efficacy Variables**

#### **5.3.3.1 Period 1 Variables**

##### **5.3.3.1.1 Primary Variables**

The primary endpoint in Period 1 is the proportion of subjects achieving ACR50 response at Week 12 (US/FDA regulatory purposes) or the proportion of subjects achieving Clinical Remission (CR) (EU/EMA regulatory purposes) at Week 24. For Japan/PMDA regulatory purposes, the primary endpoints are the proportion of subjects achieving ACR20 response at Week 12 and change from baseline in modified Total Sharp Score (mTSS) at Week 24. Analyses will be conducted separately for US/FDA, EU/EMA and Japan/PMDA regulatory purposes; the primary endpoint is specified separately for each set of analyses.

ACR20/50 response rate will be determined based on 20%/50% or greater improvement in TJC and SJC and  $\geq 3$  of the 5 measures of Patient's Assessment of Pain (VAS), Patient's Global Assessment of Disease Activity (VAS), Physician's Global Assessment of Disease Activity (VAS), HAQ-DI, or hsCRP.

CR is defined as Disease Activity Score (DAS)28 (C-reactive protein [CRP])  $< 2.6$ . DAS28 (CRP) score will be determined based on a continuous scale of combined measures of TJC, SJC, Patient's Global Assessment of Disease Activity (PtGA) (in mm), and hsCRP (in mg/L) at Week 24.

$$\text{DAS28 (CRP)} = 0.56 \times \sqrt{(\text{TJC28}^*)} + 0.28 \times \sqrt{(\text{SJC28}^{**})} + 0.36 \ln(\text{hsCRP}^{\&} + 1) + 0.014 \times \text{PtGA}^{\text{b}} + 0.96$$

\* TJC28 refers to the Subject's total Tender Joint Count out of the provided 28 evaluated joints.

- \*\* SJC28 refers to the Subject's total Swollen Joint Count out of the provided 28 evaluated joints.
  - & hsCRP refers to the high-sensitivity c-reactive protein lab value. hsCRP unit in the DAS28 (CRP) equation is expressed as mg/L.
  - » PtGA refers to the Patient's Global Assessment of Disease Activity.
- where  $\sqrt{\quad}$  is square root and  $\ln$  is natural log.

Modified Total Sharp Score (mTSS) is the van der Heijde mTSS.

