## Appendix J. Patient's Global Assessment of Disease Activity Example

### Visual Analog Scale (VAS)

VAS will be used to assess the subject's global assessment of disease activity. Each VAS consists of a horizontal 100 mm line anchored at either end by opposite adjectives reflecting the spectrum/severity of the parameters assessed:

- *Subject's global assessment of disease activity (within last 24 hours)*  
The subject will rate the severity of the RA symptoms and how he/she is doing from 0 to 100. This assessment will be used for the DAS28 (CRP) calculation in this study (see example below):

Please place a vertical mark on the line below to indicate how well your rheumatoid arthritis has been doing during THE LAST 24 HOURS:

0  
Very Well

---

100  
Very Poorly

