9.5.8 Clinical Disease Activity Index (CDAI)

CDAI is a composite continuous index to assess disease activity without using hsCRP measurement. It can be calculated based on TJC28, SJC28, Patient's Global Assessment of Disease Activity (PtGA) (in cm, 0 – 10) and Physician's Global Assessment of Disease Activity (PhGA) (in cm, 0 – 10). It can be derived as follows:

$$\text{CDAI} = \text{TJC28} + \text{SJC28} + \text{PtGA (cm)} + \text{PhGA (cm)}.$$

To calculate observed CDAI scores, the observed component value will be calculated first. Then the components will be included in the calculation per the CDAI formula selected. If any observed component is missing in a window, then the observed CDAI score will be missing.

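### The protocol's Week 26 CDAI formula gives no unit for global scores recorded on 0-100 scales, while the SAP uses 0-10 cm with the same 2.8 cut-off; the unit used in practice needs confirming

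*Protocol*

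**What the plan says.** Protocol 5.3.1.1, under CDAI, assigns the Week 26 calculation to the IRT: "An Interactive Response Technology (IRT) will calculate CDAI with input from site personnel on joint counts" and on the two global scores. It adds that "A worksheet will be provided to capture the components required for IRT entry to obtain the CDAI calculation". The formula follows the words "The calculation used to determine CDAI score at Week 26 is as follows" and is a plain sum of TJC28, SJC28, PtGA and PhGA. No unit or divisor appears.

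The protocol describes both globals on a 0-100 scale along a 100 mm line. For the physician's score, section 5.3.1.1 has the physician "rate global assessment of subject's current disease activity ranging from 0 to 100", and Appendix G repeats this. For the patient's score, Appendix J says: "The subject will rate the severity of the RA symptoms and how he/she is doing from 0 to 100". No cm or 0-10 scale for either global appears in the protocol. The only PtGA unit it attaches to a formula is in the DAS28 definition (5.3.3.1.1): "Patient's Global Assessment of Disease Activity (PtGA) (in mm), and hsCRP (in mg/L) at Week 24".

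The SAP also records both scales as 0-100 mm (9.5.3, 9.5.4). Its CDAI definition (9.5.8) nevertheless enters PtGA in cm, 0-10, and likewise "Physician's Global Assessment of Disease Activity (PhGA) (in cm", 0-10. Both documents set CDAI remission at 2.8 or below (protocol 5.2.3.3 and 5.3.3.1.3; SAP 4.2 and 9.5.9).

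**The concern.** Whether a subject is in CDAI remission at Week 26 decides whether blinded treatment continues without protocol-directed change. A subject not in remission goes to one of two branches. One is optimization of background medication, for those with at least 20% improvement in both joint counts. The other is a change of study treatment, for those without it. A tenfold difference in two of the four terms, against an unchanged cut-off, gives different answers for the same subject.

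The calculation also crosses systems. The globals are captured on the ePRO tablet (protocol 10.2), but the Week 26 CDAI comes from the IRT, using values that site staff supply through a worksheet. A scale error could enter at that transfer, and the protocol gives sites no unit to check against.

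The analyses still to come could be touched through SAP 8.1. It censors upadacitinib monotherapy exposure when a background csDMARD is added, and it ties such additions after Week 26 to the CDAI response and joint counts. Those exposure groups carry the long-term adverse event rates (SAP 10.1.2, 10.2.2).

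**Working it through.** The plan has no derived figure to reproduce here; 2.8 is a threshold. The check applies both written formulas to the same scores.

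**Inputs.** TJC28 and SJC28 each run 0-28. PtGA and PhGA run 0-100 mm as recorded. The cut-off is 2.8. Let k = TJC28 + SJC28 and g = PtGA + PhGA in mm.

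- Protocol, read literally: CDAI = k + g, range 0 to 28 + 28 + 100 + 100 = 256.
- SAP 9.5.8: CDAI = k + g/10, range 0 to 28 + 28 + 10 + 10 = 76.

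**Direction.** The literal protocol value exceeds the SAP value by 0.9 × g, which is never negative. A subject can be in remission by the SAP and not by the protocol, but never the reverse.

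**Room left for the globals.** Remission requires g ≤ 10 × (2.8 − k) by the SAP and g ≤ 2.8 − k by the literal protocol. The combination counts use whole millimetres.

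| k | Max g, SAP | Max g, literal protocol | Combinations, SAP | Combinations, literal protocol |
|---|---|---|---|---|
| 0 | 28 mm | 2 mm | 435 | 6 |
| 1 | 18 mm | 1 mm | 2 × 190 = 380 | 2 × 3 = 6 |
| 2 | 8 mm | 0 mm | 3 × 45 = 135 | 3 × 1 = 3 |
| Total | | | 950 | 15 |

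So 950 − 15 = 935 combinations (935/950 = 98.4%) change class. This counts possible scores with equal weight and does not estimate a share of subjects.

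**Examples.**
- k = 0, globals 10 and 10 mm: 0 + 1.0 + 1.0 = 2.0 by the SAP; 0 + 10 + 10 = 20 by the protocol text.
- k = 1, globals 9 and 9 mm: 1 + 0.9 + 0.9 = 2.8 by the SAP; 1 + 9 + 9 = 19 by the protocol text.
- k = 0, globals 1 and 2 mm: 0.3 by the SAP; 3 by the protocol text.

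**Which branch a flipped subject would enter.** Such a subject has k ≤ 2. A change of study treatment also requires failing 20% improvement in TJC or SJC. Assume that this criterion uses the full 68/66 counts, and ignore extrapolation for unassessed joints. Entry needs at least 6 tender and 6 swollen joints. From a baseline of 6, 20% improvement means 0.8 × 6 = 4.8 or fewer, so failing means 5 or more. At most 2 of those 5 can lie in the 28-joint set, so at least 5 − 2 = 3 must lie outside it. In that limiting case k = 2 and g is at most 8 mm. A higher baseline demands more joints outside the set. Nearly all flipped subjects would therefore meet the joint criterion and enter the background-medication branch.

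**The case against.** The strongest reply is that the protocol omits a unit and does not prescribe mm. Silence does not forbid conversion. The mm in the DAS28 definition does not carry over: the SAP uses mm for DAS28 and cm for SDAI and CDAI, so the unit belongs to the index. The cut-offs also suggest that 0-10 scaling was meant. CDAI of 10 or below for low disease activity and 2.8 or below for remission stand beside SDAI limits of 11.0 and 3.3, and SAP 6.1 puts high disease activity above 22. The SAP, which says it elaborates the protocol's methods, supplies the unit.

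Most of this stands, and it rules out two stronger conclusions that a reader might draw.

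- *That subjects were in fact misclassified.* The IRT made the calculation from a worksheet that is not in the documents, so this cannot be known from them.
- *That treatment path and analysis classification broadly disagree, with later data wrongly set to failure or carried forward.* SAP 9.3.1 applies post-Week 26 NRI and LOCF to rescue switchers, who must miss CDAI remission **and** fail the joint-count criterion. Week 48 extrapolation (SAP 9.3.2) uses the same rescue-switching criteria. In the first example, if the full joint counts are also zero, improvement is 100% and the subject is not a switcher under either unit.

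What does not stand is treating this as cosmetic. The formula is presented as the operative one for a treatment decision, every scale the protocol gives for its inputs is 0-100, and the literal result makes remission almost unattainable.

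**Conclusion.** The inconsistency is real and worth correcting. As written, the protocol and SAP formulas give different CDAI values for any subject with a non-zero global score, and they disagree on remission for 935 of the 950 whole-number combinations that qualify under the SAP. The disagreement always runs toward non-remission under the protocol text.

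The consequence is conditional on the IRT having summed unconverted scores. In that case, subjects in remission by the SAP formula would have been sent to background-therapy optimization. A csDMARD is one option there, and adding one ends upadacitinib monotherapy exposure under SAP 8.1. The later rates would still reflect treatment received; what would change is who remains in the monotherapy groups and for how long. Effects on treatment switching, on post-Week 26 NRI and LOCF, and on Week 48 extrapolation would be small, because the joint-count criterion must also fail.

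The Week 12 and Week 24 primary and ranked endpoints precede the decision and are unaffected. Period 1 reporting is complete (SAP 11.1), so what remains is verification, documentation and the long-term reporting.

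**What to change.** 1. Reconcile protocol 5.3.1.1 (CDAI) with SAP 9.5.8 by stating one unit for PtGA and PhGA in both. Which unit applies is for the sponsor to settle against the IRT specification.
2. Confirm and file the unit that the IRT and the site worksheet used at Week 26.
3. If it differs from SAP 9.5.8, base the Week 26 rescue classification on the actual IRT assignment instead of a re-derived CDAI. Report the number of subjects whose IRT and SAP classifications disagree, by randomized group and by branch entered.

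The cost is one line of protocol text and one specification check. If step 3 is needed, add one tabulation from Week 26 joint counts and global scores already collected. No new data are required.
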